2.3. Study/Dose Rationale

2.3.1. Study Rationale

Nintedanib (BIBF 1120) is an oral tyrosine kinase inhibitor of VEGFR. It has demonstrated evidence of anticancer activity in lung and ovarian cancer in clinical trials, and is undergoing further investigation in metastatic colorectal cancer. Given the analogies between appendiceal and colorectal cancer and potentially ovarian cancer, and the limited information about the optimal treatment of metastatic appendiceal carcinomas, further investigation with nintedanib is warranted in this disease.

2.3.2. Dose Rationale

The dose of nintedanib was selected based on doses evaluated in single agent and combination studies in patients with cancer, or others with idiopathic fibrosis. The most extensive experience with nintedanib in patients with malignancy is in lung cancer. Nintedanib was evaluated at 150 mg twice daily and 250 mg twice daily in patients with stage IIIB and IV non-small cell lung cancer (NSCLC) after first or second line platinum based chemotherapy in a randomized phase II study. They reported no clear difference in efficacy, though the only confirmed partial response was at the 250 mg BID dose. It did appear that patients receiving the higher dose did experience more frequent grade 3-4 elevations in transaminases and GGTP, diarrhea and nausea. Interestingly, no grade 3 or 4 hypertension was reported¹³. Thus, a phase 3, double-blind, placebo-controlled study was performed in 1314 patients with NSCLC in the second line setting, comparing docetaxel with 200 mg po BID of nintedanib with docetaxel and placebo. This study demonstrated that the addition of nintedanib to docetaxel significantly improved the median progression free survival, compared to docetaxel and placebo (3.5 months, compared to 2.7 months), meeting the study's primary endpoint. Even in combination with docetaxel, nintedanib was fairly well tolerated, with the most common severe toxicities again being diarrhea, and transaminase elevations¹⁰. In two large randomized, double-blind phase 3 studies totaling 1066 patients with idiopathic pulmonary fibrosis, nintedanib 150 mg twice daily was compared to placebo, and proved to be well tolerated, with the most common toxicities being diarrhea and elevations in the liver enzymes, but less than 5%

of patients discontinued nintedanib because of toxicities. However, it should be noted that five patients (1.6%) had a myocardial infarction while on nintedanib, compared to one (0.5%) who was treated with placebo¹⁹. Taken together, this data suggests that nintedanib at doses from 150 to 200 mg, and perhaps 250 mg twice daily is tolerable, and should be investigated at a dose of 200 mg twice daily as a single agent in the second line setting.

3. BENEFIT/RISK ASSESSMENT

Although considerable progress has occurred in understanding the biological characteristics of cancer as well as the development of more effective treatment regimens, most patients with locally advanced or metastatic tumors succumb to their disease. Thus, there is a substantial need for novel therapeutic strategies to improve the outcome for patients with advanced or metastatic appendiceal carcinoma.

Antiangiogenic treatment with the orally available triple angiokinase inhibitor nintedanib with inhibition of VEGFR, PDGFR and FGFR offers the chance to control both locally recurrent and distant metastatic disease on an outpatient basis. Treatment with nintedanib may have the potential to provide significant benefit to patients with locally advanced and/or metastatic appendiceal carcinoma by slowing tumor progression and metastasis, since its cellular target is expressed on the tumor vasculature in most malignancies. Induction of endothelial cell apoptosis may result in subsequent degradation of tumor vessels and subsequent tumor necrosis. Additionally tumor growth may be affected by direct anti-tumor effects, e.g. tumor cells that express VEGFR, PDGFR, or FGFR.

The main risks of therapy with nintedanib in adult patients are:

- the gastro-intestinal AEs (diarrhea nausea, vomiting, abdominal pain)
- increases in liver enzymes (AST, ALT, ALKP) and bilirubin
- Perforation (gastrointestinal and non-gastrointestinal)
- Hypertension
- Venous thromboembolism
- Bleeding
- Neutropenia and sepsis, if combined with myelosuppressive chemotherapy
- Pancreatitis

Liver enzymes must be followed closely during treatment with nintedanib.

Therapy with the trial drug must be interrupted in the event of relevant elevations of liver enzymes and/or of bilirubin and further treatment is to be withheld until recovery of the abnormal laboratory parameters.

Hypertension is a side effect of nintedanib and a slightly increased frequency of hypertension has been observed in the trials with nintedanib to a mild to moderate degree and only few cases of CTCAE grade 3 or 4 hypertension have been observed. With respect to bleeding, in the LUME –Lung 1 trial involving 1314 patients more bleeding events were reported for nintedanib-treated squamous cell carcinoma patients (all grades: 17.1% vs. 10.9%; grade ≥ 3 : 2.9% vs. 1.3%) than for those with adenocarcinoma (all grades: 10.9% vs. 11.1%; grade ≥ 3 : 1.5% vs. 1.3%). Fatal bleeding events were balanced between both arms regardless of histology.

Based upon a non-clinical safety study *in vitro*, nintedanib may have a potential risk of phototoxicity (skin and eyes) *in vivo*. Few cases of photosensitivity reactions (less than 1 %) and of CTCAE grade 1 intensity only have been reported from the clinical studies to date. If adequate precautions are taken (avoidance of prolonged ultraviolet exposure, use of broad spectrum sunscreen and sunglasses), treatment with nintedanib is considered safe.

4. SUBJECT SELECTION

4.1. Accrual

This study will enroll up to 39 subjects in 2 stages with appendiceal carcinoma that have failed (defined as progression on or within 6 months or intolerance of) initial fluoropyrimidine-based chemotherapy. It is anticipated the duration of accrual will be 48 months. Both men and women of all races and ethnic groups are eligible for this trial.

4.2. Eligibility Criteria

4.2.1. Inclusion Criteria

Subjects must meet all of the following criteria:

- a. Age \geq 18 years old
- b. Histologically confirmed appendiceal carcinoma stage IV
- c. Failure of initial fluoropyrimidine -based chemotherapy. Failure is defined as progression on or within 6 months of last day of therapy or intolerance of initial fluoropyrimidine-based chemotherapy.
- d. Life expectancy at least 3 months
- e. ECOG performance status score 0-2

- f. Presence of measurable and/or evaluable, non-measurable disease according to RECIST 1.1 criteria
- g. Written informed consent signed and dated by subject or Legally Authorized Representative (LAR) prior to admission to the study in accordance with ICH-GCP guidelines and to the local legislation.

4.2.2 Exclusion Criteria

Subjects must not meet any of the following criteria.

- a. Prior treatment with nintedanib or any other VEGFR inhibitor
- b. Known hypersensitivity to peanut or soya or to contrast media. History of hypersensitivity to contrast media is allowed if the subject is able to tolerate contrast media with pre-medication.
- c. Chemo-, hormone-, radio-(except for brain and extremities) or immunotherapy or therapy with monoclonal antibodies or small tyrosine kinase inhibitors within the past 4 weeks prior to treatment with the trial drug.
- d. Radiotherapy to any target lesion within the past 3 months prior to baseline imaging when that target lesion is the only target lesion identified on baseline imaging, unless it has subsequently grown.
- e. Persistence of clinically relevant therapy related toxicity from previous chemo and/or radiotherapy as determined by the investigator.
- f. Active brain metastases (e.g. stable for <4 weeks, no adequate previous treatment with radiotherapy, symptomatic, requiring treatment with anti-convulsants; dexamethasone therapy will be allowed if administered as stable dose for at least one month) or leptomeningeal disease.
- g. Radiographic evidence of cavitory or necrotic tumors.
- h. Tumors with radiographic evidence (CT or MRI) of local invasion of major blood vessels.
- i. Anti-neoplastic treatment for appendiceal cancer, with other investigational drugs or treatment in another clinical trial within 30 days before start of study treatment.
- j. Therapeutic anticoagulation with drugs requiring INR monitoring (except low-dose heparin and/or heparin flush as needed for maintenance of an in-dwelling intravenous device) or anti-platelet therapy (except for low-dose therapy with acetylsalicylic acid \leq 325mg per day).

- k. Major injuries and/or surgery within the past 4 weeks prior to start of study treatment, incomplete wound healing or planned surgery during the on-treatment study period.
- l. History of clinically significant hemorrhagic or thromboembolic event in the past 6 months prior to consent.
- m. Known inherited predisposition to bleeding or thrombosis.
- n. Significant cardiovascular diseases (i.e. uncontrolled hypertension, unstable angina, history of infarction, congestive heart failure > NYHA II, serious cardiac arrhythmia, pericardial effusion) within the past 12 months prior to start of study treatment.
- o. Proteinuria CTCAE grade 2 or greater.
- p. Creatinine > 1.5x ULN or GFR < 45 ml/min.
- q. Hepatic function: total bilirubin above normal limits; ALT or AST > 1.5x ULN in subjects without liver metastasis. For subjects with liver metastasis: total bilirubin above normal limits; ALT or AST > 2.5x ULN.
- r. Coagulation parameters: International normalised ratio (INR) > 2x ULN, prothrombin time (PT) and partial thromboplastin time (PTT) \geq 1.5x ULN.
- s. Absolute neutrophil count (ANC) < 1500/ml, platelets < 100000/ml, Hemoglobin < 9.0 g/dl.
- t. Other malignancies at the time of signing the informed consent other than basal cell skin cancer or carcinoma in situ of the cervix.
- u. Active serious infections if requiring systemic antibiotic or antimicrobial therapy.
- v. Active or chronic hepatitis C and/or B infection.
- w. Gastrointestinal disorders (like chronic diarrhea) or abnormalities that would interfere with absorption of the study drug per investigator discretion. Subjects with this disorder may be allowed if able to tolerate anti-diarrheal medications like loperamide.
- x. Serious illness or concomitant non-oncological disease such as neurologic, psychiatric, infectious disease or active ulcers (gastro-intestinal tract, skin) or laboratory abnormality that may increase the risk associated with study participation or study drug administration and in the judgment of the investigator would make the subject inappropriate for entry into the study.
- y. Sexually active women of child-bearing potential and men who are sexually active with women of child-bearing potential and unwilling to use at least 2 medically acceptable method of contraception (e.g. such as implants,

injectables, combined oral contraceptives, some intrauterine devices or vasectomized partner for participating females, condoms for participating males) during the trial and for at least three months after end of active therapy. Female subjects will be considered of child-bearing potential unless surgically sterilized by hysterectomy or bilateral tubal/salpingectomy, or post-menopausal for at least 2 years.

- z. Pregnancy or breast feeding; female participants of child-bearing potential must have a negative pregnancy test (β -HCG test in urine or serum) before commencing study treatment.
- aa. Psychological, familial, sociological, or geographical factors potentially hampering compliance with the study protocol and follow-up schedule per the investigator.
- bb. Alcohol or drug abuse which in the determination of the investigator would interfere with trial participation.
- cc. Significant weight loss, (> 10% of baseline weight) within past 2 months prior to consenting for the trial. Removal of ascites should not be calculated as weight loss. For subjects who have had ascites removed within the 2 months prior to consent, the S-I should be consulted.

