- Palliative radiation therapy is allowed if the target lesion(s) are not included within the radiation field and no more than 10% of the bone marrow is irradiated.
- Granulocyte colony-stimulating factor (G-CSF) and other hematopoietic growth factors may be used in the management of acute toxicity, such as febrile neutropenia, when clinically indicated or at the Investigator's discretion. However, they may not be substituted for a required dose reduction. Subjects are permitted to take chronic erythropoietin.
- Treatment with nonconventional therapies (such as acupuncture), and vitamin/mineral supplements are permitted provided that they do not interfere with the study endpoints, in the opinion of the Investigator.
- Bisphosphonates.
- Subjects taking narrow therapeutic index medications should be monitored proactively (e.g. phenytoin, quinidine, carbamazepine, phenobarbital, cyclosporine, and digoxin).

Laboratory Tests. The blood-based clinical laboratory tests at screening will include a complete blood count with differential and platelets, a comprehensive metabolic panel (including sodium, potassium, chloride, bicarbonate, BUN, creatinine, glucose, and calcium, albumin, alkaline phosphatase, ALT (SGPT), AST (SGOT), total bilirubin, direct bilirubin only if total bilirubin is above normal, and total protein), PTT, PT/INR and urinalysis (UA). After enrollment, a complete blood count with

differential and platelets and a comprehensive metabolic panel (including sodium, potassium, chloride, bicarbonate, BUN, creatinine, glucose, calcium, albumin, alkaline phosphatase, ALT (SGPT), AST (SGOT), total bilirubin, direct bilirubin only if total bilirubin is above normal and total protein) will be performed according to the Study Calendar.

Correlative Studies. Ascites will be removed from the subject when required as a part of standard of care and the entire volume that is removed for clinical purposes and remaining after any diagnostic tests will be processed to concentrate any cells and create a cell block(s) by CHS Pathology. The ascites cell block will be banked and stored at room temperature at the BSR for VEGF levels and for future assays.

Serum (2- 10 ml tubes) specimens from subjects and will be processed within one hour of collection, if possible, but may be kept at 4°C for no longer than 4 hours before processing. Serum will be processed and stored at -80°C until future testing. Specimens will be stored at the CHS Biospecimen Repository.

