Specimens will be collected according to the schedule in Section 6. Specimens will be collected after subject eligibility confirmation, but prior to administration of the first dose of nintedanib and subsequent cycles. Exploratory biomarker arrays may be used.

Radiology and Tumor Measurements. A computed tomography (CT) scan with oral and intravenous contrast of the chest, abdomen and pelvis will be performed within 28 days prior to the first dose of nintedanib (screening scan). Scans will then be performed within 7 days following anticipated completion of cycle 2 unless clinically proven otherwise and within 7 days of anticipated completion of every two cycles thereafter (e.g. end of cycles 4, 6). A contrast-enhanced MRI of the abdomen and pelvis and a CT scan of the chest without contrast may be substituted if clinically necessary; however, subsequent studies must be performed using the same imaging modality throughout the study period.

For subjects who discontinue study therapy due to toxicity or reasons other than progressive disease, every effort will be made to obtain imaging studies and tumor assessments every 8 weeks (+/- 2 weeks) until documented progression or the start of subsequent anti-cancer therapy.

Subsequent Therapy and Survival Status. Once subjects complete their End of Treatment visit, they will be followed until all treatment-related toxicities have resolved, returned to baseline, stabilized, or are deemed irreversible. Subject's initial anti-cancer therapy following discontinuation of nintedanib treatment and survival

status will be documented.

Subjects (or their family members or designees) may be contacted by telephone, in writing, or during clinic visits after treatment discontinuation for collection of long-term follow-up data approximately every 6 months until death or lost to follow-up, or until the criteria defined for the final analysis (Section 13.3.1) are reached. However, in the event the criteria for the final analysis are met, and there are subjects who have not yet been discontinued from nintedanib treatment, subjects in follow up will continue to be followed until all subjects have discontinued study treatment and completed the safety monitoring period. Long-term follow-up clinical information may also be obtained through chart reviews.

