12.1.2. Response Criteria

Response will be evaluated using RECIST 1.1 Criteria.

Complete Response:

- Target lesion: Disappearance of all target lesions. Any pathological lymph nodes (whether target or non-target) must have reduction in short axis to <10 mm.
- Non-target lesion: Disappearance of all non-target lesions. All lymph nodes must be non-pathological in size (<10 mm short axis).

Partial Response:

- Target lesion: At least a 30% decrease in the sum of diameters of target, taking as reference the baseline sum diameters.
- Non-target lesion: Not applicable

Stable Disease:

- Target lesion: Neither sufficient shrinkage to qualify for a partial response, nor sufficient increase to qualify for progressive disease, taking as reference the smallest sum diameters while on study.
- Non-target lesion: Not applicable.

Progressive Disease:

- Target lesion: At least a 20% increase in the sum of diameters of target lesions, taking as reference the *smallest sum on study* (this includes the baseline sum if that is the smallest on study). In addition to the relative increase of 20%, the sum must also demonstrate an absolute increase of at least 5 mm. (*Note:* the appearance of one or more new lesions is also considered progression).
- Non-target lesion: *Unequivocal progression* (as described in RECIST version 1.1) of existing non-target lesions. (*Note:* the appearance of one or more new lesions is also considered progression).

Non-Complete Response / Non-Progressive Disease:

- Target lesion: Not applicable
- Non-target lesion: Persistence of one or more non-target lesion(s)

Table 6: Summary of RECIST

Target Lesions	Non-target Lesions	New Lesions	Overall Response	Best Response for this Category also requires
CR	CR	No	CR	Documented at least once ≥ 4 weeks from baseline
CR	Non-CR/Non-PD	No	PR	Documented at least once ≥ 4 weeks from baseline
CR	Not evaluated	No	PR	
PR	Non-PD or not all evaluated	No	PR	
SD	Non-PD or not all evaluated	No	SD	Documented at least once ≥ 4 weeks from baseline
Not all evaluated	Non-PD	No	NE	N/A
PD	Any	Yes or No	PD	No prior SD, PR or CR
Any	PD*	Yes or No	PD	
Any	Any	Yes	PD	
* In exceptional circumstances, unequivocal progression in non-target lesions may be accepted as disease progression CR = Complete Response, PR = Partial Response, SD = Stable Disease, PD = Progressive Disease, and NE = inevaluable				

Table 7: Overall Response for Subjects with Non-measurable disease only

Non-target Lesions	New Lesions	Overall Response

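### A recently irradiated lesion may be a target lesion whenever there is a second target, so a radiotherapy after-effect can be counted as disease control

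*Combined protocol and SAP*

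**What the plan says.** - **Section 4.2.2, criterion d.** Radiotherapy to a target lesion within 3 months before baseline imaging excludes a subject only "when that target lesion is the only target lesion identified on baseline imaging, unless it has subsequently grown". The criterion therefore assumes that such a lesion can be a target.
- **Section 4.2.2, criterion c.** This sets a general washout before trial drug: "Chemo-, hormone-, radio-(except for brain and extremities) or immunotherapy or therapy with monoclonal antibodies or small tyrosine kinase inhibitors within the past 4 weeks".
- **Section 5.5, imaging.** The baseline CT "will be performed within 28 days prior to the first dose of nintedanib (screening scan").
- **Section 5.5, concomitant therapy.** During the study, "Palliative radiation therapy is allowed if the target lesion(s) are not included within the radiation field". This rule covers radiation given on study only.
- **Section 12.1.2.** PR is "At least a 30% decrease in the sum of diameters of target, taking as reference the baseline sum diameters". PD is "At least a 20% increase in the sum of diameters of target lesions", measured from the smallest sum on study and with an absolute rise of at least 5 mm. In addition, "the appearance of one or more new lesions is also considered progression". The section has no separate provision for irradiated lesions.
- **Sections 13.1.1 and 13.2.** In measurable disease, a best overall response of CR, PR or SD is a success, and every subject who starts nintedanib counts. Table 6 asks for SD to be documented once, at least 4 weeks from baseline.

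**The concern.** Criterion d recognises that a lesion irradiated recently and not grown since is a poor gauge of drug effect, but it acts on this only when there is a single target. With two or more targets, the lesion can enter the sum on equal terms with the others. The plan keeps target lesions out of the field of on-study radiation, yet gives no matching protection against radiation given just before entry.

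The trial has one arm and compares its disease control rate with an inferred 30%. One qualifying SD assessment makes a subject a success. If an irradiated lesion is still shrinking after the baseline scan, or is held static, it can keep the sum below the PD threshold while other targets grow. No control arm would carry the same effect, and no sensitivity analysis is planned that would show it.

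**Working it through.** **1. The plan's own design (Section 13.1).** Inputs: 28 subjects in stage 1, continue at 8 or more; 39 in total, reject at 16 or more; null rate 0.30, alternative 0.50, one-sided 0.10.

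P(reject | p) = Σ over x = 8..28 of Bin(x; 28, p) × P(Bin(11, p) ≥ 16 − x)

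- p = 0.30: 0.0943 (stated 0.10)
- p = 0.50: 0.9001 (stated at least 90%)

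The design reproduces and is not in question.

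**2. The open window.** Criterion c removes the 4 weeks before first dose, except for brain and extremities. Criterion d looks back 3 months from a baseline scan taken up to 28 days before first dose. What remains is radiotherapy from about 4 weeks to about 3 to 4 months before first dose, in subjects with at least two targets. Outside brain and extremities the baseline scan follows such radiotherapy, so only change after that scan can count.

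**3. Masked progression, worked example.** Targets at baseline: 40 mm (irradiated) and 30 mm (not irradiated), sum 70 mm. At the first scan the untreated lesion measures 50 mm. There are no new lesions and no non-target progression.

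- Irradiated lesion static: 40 + 50 = 90 mm; (90 − 70)/70 = +28.6%, a rise of 20 mm. This is PD, a failure.
- Irradiated lesion down to 28 mm: 28 + 50 = 78 mm; (78 − 70)/70 = +11.4%. This is SD, a success.

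The PD threshold is 1.20 × 70 = 84 mm. The untreated lesion reaches it at 84 − 40 = 44 mm in the first case and at 84 − 28 = 56 mm in the second. Between 44 and 56 mm, the shrinkage of the irradiated lesion alone changes the outcome.

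In general, if the irradiated lesion is a share w of the baseline sum and shrinks by a fraction s, the other targets reach the threshold when they have grown by g = (0.20 + w·s)/(1 − w). At w = 0.5:

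- s = 0: g = 40%
- s = 0.30: g = 70%
- s = 0.50: g = 90%

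**4. Partial response.** With the other targets unchanged, PR needs s ≥ 0.30/w: 60% shrinkage at w = 0.5, 43% at w = 0.7, complete disappearance at w = 0.3, impossible at w = 0.2. Disease control is therefore the more plausible route.

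**5. Effect on the type I error.** The documents do not give the share f of affected subjects or their probability q of disease control without drug effect. Both are assumed here. The null rate becomes p* = 0.30(1 − f) + q·f, which goes into the formula in step 1.

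| f | q | p* | Type I error |
|---|---|---|---|
| 0 | – | 0.300 | 0.094 |
| 1% | 0.5 | 0.302 | 0.099 |
| 1% | 1.0 | 0.307 | 0.112 |
| 2% | 0.5 | 0.304 | 0.104 |
| 2% | 1.0 | 0.314 | 0.132 |
| 5% | 0.5 | 0.310 | 0.120 |
| 5% | 1.0 | 0.335 | 0.203 |

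For scale, 5% of 39 is 0.05 × 39 = 1.95 subjects.

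**The case against.** The sponsor considered recent radiotherapy and drew a line at the sole target, and several provisions narrow what is left. Criterion c removes the latest 4 weeks. Its exception for brain and extremities matters little, because protocol imaging covers chest, abdomen and pelvis and active brain metastases are excluded. Shrinkage already present on the baseline scan earns nothing. New lesions and unequivocal non-target progression are PD whatever the sum does. Section 2.1 describes a peritoneal disease treated with systemic therapy and does not mention radiotherapy for it, so affected subjects may be very few. All of this stands, and it limits the size of the problem. It does not close the gap, because none of these rules catches growth in another target that the sum conceals.

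A second objection is that RECIST 1.1 is adopted by reference and may itself restrict irradiated lesions. The documents do not reproduce such a rule, and criterion d is worded as though these lesions can be targets. A sentence in the protocol would settle it either way.

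A reader might also infer that any SD in a subject with an irradiated target is owed to radiotherapy. That is wrong. With the same two lesions, if the untreated one grows only from 30 to 36 mm and the irradiated one is static, the sum is 76 against 70 mm (+8.6%). That is SD without any shrinkage, simply because two lesions are summed.

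**Conclusion.** The gap is real on the text: the after-effect of pre-study radiotherapy can be counted as disease control when there are two or more targets. The documents do not support saying that it is so counted, because they do not show that any such subject will enrol.

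The range of 0.099 to 0.203 for the type I error rests entirely on the assumed f of 1% to 5% and q of 0.5 to 1.0; at the low end it stays below the nominal 0.10. A reader might prefer a single figure: one subject made a certain success raises the type I error to 0.137, and two raise it to 0.193. Those figures presuppose false successes at a frequency the documents do not give, so they should not be quoted as the trial's error rate. Nor does the point show that the sample size or the cut-offs are wrong. It is a modest, inexpensive correction to target selection, worth making because the trial has no control arm and one SD assessment is enough for success.

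**What to change.** - **Section 12.1.** Add that, when other measurable lesions exist, a lesion irradiated within 3 months before baseline imaging and without documented growth since may not be selected as a target lesion and is followed as non-target. Its unequivocal progression then still counts as PD.
- **Criterion d.** Reword it to match, for example so that it applies when the irradiated lesion is the only lesion that could serve as a target lesion. Left as it is, d might never trigger if such a lesion were no longer regarded as a target, and subjects it now excludes could enter under inclusion criterion f as non-measurable disease, where a single non-progressive assessment is a success. The sponsor should also say what happens when two or more measurable lesions exist and all were irradiated in the window; d does not exclude that subject today.

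The cost is wording. No imaging is added, and the sample size and decision rule stay as they are. A few subjects will have fewer target lesions, so their response rests on a smaller sum. In the example, PD would be reached when the untreated lesion measures 36 mm (30 × 1.20, a rise of 6 mm) instead of 44 mm with a static irradiated lesion.
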